#### 3.2 Sample Size

An approximate total of **310** subjects will enroll into this study such that the long-term safety, **tolerability** and efficacy of AMG 145 among subjects with severe familial hypercholesterolemia can be assessed. Enrollees will be comprised of subjects from study 20110233 or qualifying Amgen protocol as well as subjects with severe familial hypercholesterolemia due to genetic causes beyond those studied in the parent (eg, gain of function mutations in PCSK9). Finally, we will also include additional subjects with homozygous familial hypercholesterolemia. If these subjects are ineligible for participation into an AMG 145 protocol they may be considered for participation; they otherwise must wait after study 20110233 has been closed.

The 95% confidence intervals for an approximate 5% incidence rate under various sample sizes using the binomial distribution for particular adverse events are provided in the table below.

	Total Number of	Estimated Adverse Event Incidence Rate		
Sample size	Subjects Reporting Adverse Event	Incidence Rate	95% Confidence Interval	
300	15/300	5%	(3%, 7%)	
310	16/310	5.2%	(3%, 8%)	
320	16/320	5%	(3%, 7%)	

# 4. Study Endpoints

# 4.1 Primary Endpoint

Subject incidence of treatment emergent adverse events.

# 4.2 Secondary Endpoints

- Percent change in LDL-C from baseline at each scheduled visit
- Percent change in non-HDL-C from baseline at each scheduled visit
- Percent change in Lp(a) from baseline at each scheduled visit
- Percent change in ApoB from baseline at each scheduled visit
- Percent change in total cholesterol/HDL-C ratio from baseline at each scheduled visit

Statistical Analysis Plan: 20110271

Dated: 26 May 2018 Page 8 of 27

Percent change in ApoB/ApoA1 ratio from baseline at each scheduled visit

 Response rate of subjects with 15% or greater reduction in LDL-C from baseline by scheduled visit

# 4.3 Exploratory Endpoints

- Subject incidence of adjudicated events
  - death by any cause
  - cardiovascular death
  - myocardial infarction
  - hospitalization for unstable angina
  - coronary revascularization
  - stroke
  - transient ischemic attack (TIA)
  - hospitalization for heart failure
- Subject incidence of non-coronary revascularization

## Lipid and other efficacy laboratory parameters:

- Percent change from baseline at each scheduled visit in the following parameters:
  - Total cholesterol
  - VLDL-C
  - HDL-C
  - ApoA1
  - Triglycerides
- Change from baseline at each scheduled visit in the following parameters:
  - LDL-C
  - Total cholesterol
  - non-HDL-C
  - ApoB
  - Total cholesterol/HDL-C ratio
  - ApoB/ApoA1 ratio
  - VLDL-C
  - HDL-C
  - ApoA1
  - Triglycerides
  - Lp(a)
  - PCSK9

Statistical Analysis Plan: 20110271

Dated: 26 May 2018 Page 9 of 27

#### Safety

 Changes from baseline in safety laboratory values (including clinical chemistry and hematology, HbA1c) and vital signs at each scheduled visit

Subject incidence of anti-AMG 145 antibodies (binding and neutralizing) formation

#### Pharmacokinetics

Serum concentration of AMG 145 and PCSK9 at selected time points

## 5. Hypothesis

There is no formal hypothesis testing. The **primary clinical** hypothesis is that long-term exposure of AMG 145 will be safe and well tolerated in subjects with severe familial hypercholesterolemia.

#### 6. Definitions

The study consists of four different types of subjects,

- Homozygous FH Apheresis Subjects: Subjects who either met clinical criteria
  of HoFH or who had supportive genetic information; and receiving apheresis at
  study baseline.
- Homozygous FH Non-Apheresis Subjects: Subjects who either met clinical criteria of HoFH or who had supportive genetic information; and not receiving apheresis at study baseline
- Severe Heterozygous FH Apheresis Subjects: Subjects who didn't meet clinical criteria of Homozygous FH and who had supportive genetic information; and receiving apheresis at study baseline
- Severe Heterozygous FH Non-Apheresis Subjects: Subjects who didn't meet clinical criteria of Homozygous FH and who had supportive genetic information; and not receiving apheresis at study baseline

Some of the definitions will depend on the subject type.

#### 6.1 Study Time Points

# **Baseline**

For parent study rollover subjects, baseline is defined as the baseline of the parent study.

For non-parent study subjects, baseline is defined as the time period before the first administration of AMG 145. In particular, for non-parent apheresis subjects, if an assessment was done both pre- and post-apheresis, only the assessment made pre-apheresis will be considered baseline.

Statistical Analysis Plan: 20110271

Dated: 26 May 2018 Page 10 of 27

For hemoglobin A1c, baseline is defined as the study 20110271 baseline for all subjects, as hemoglobin A1c was not collected in study 20110233.

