- Subjects from a qualifying parent study with baseline parent study data: the baseline is defined as the baseline of the parent study
- Subjects not enrolling from a parent study or without baseline parent study data: the baseline is defined as the baseline obtained in this study (study 20110271)

For non-efficacy analyses, baseline values for all subjects are defined as the baseline values obtained in this study, 20110271.

There will be no imputation for missing data.

Analysis of Primary Endpoint

Adverse events will be coded using the latest version of Medical Dictionary for Regulatory Activities (MedDRA). Subject incidences of treatment-emergent adverse events, serious adverse events, and adverse events leading to withdrawal will be tabulated by system organ class and preferred term.

[figure not shown]
Analysis of Secondary Endpoints

Secondary endpoints will be summarized at each scheduled visit. Descriptive statistics will be presented.

[figure not shown]
For a full description of statistical analysis methods, refer to [Section 10](#).

Sponsor: Amgen

Study Design and Treatment Schema

□ LDL-C reductions achieved are relative to subject's baseline LDL-C value
 □ PCSK9 levels are measured at the end of the 4 week dosing interval for subjects that have received 420 mg QM
 *Week 2 and week 10 assessments and visits are not compulsory for non-parent/nonapheresis subjects only, should not be performed for parent study subjects and are mandatory for apheresis subjects
 ^Week 9 and screening weeks -2 and -1 are for apheresis subjects only
 *Week -2 and -1 assessments are performed for all apheresis subjects.
 † Dose changes after Week 24 are discouraged, dose changes must be discussed with the medical monitor
 FH = familial hypercholesterolemia

Study Glossary

Abbreviation or Term	Definition/Explanation
ADE	Adverse device effect
Adolescent	Subjects are considered adolescent if their 18 th birthday occurs after the date of enrollment in the parent study (for parent study rollover subjects) or after the date of enrollment in Study 20110271 (for all other subjects). Other subjects are considered adults, including those whose 18th birthday coincides with the date of enrollment in the parent study or present study, as applicable
AE	Adverse event
AHA	American Heart Association
ALP	Alkaline phosphatase
ALT (SGPT)	Alanine aminotransferase (serum glutamic-pyruvic transaminase)
ApoA1	Apolipoprotein A-1
ApoB	Apolipoprotein B

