10.4 Planned Methods of Analysis

10.4.1 General Approach/Considerations

Statistical analyses in this open label study are descriptive in nature. No statistical inference or missing value imputation is planned. **The final analysis for the study will be performed at the end of the study (defined as when the last subject has completed the assessments for week 260 or until the investigator's recommendation of discontinuation, Amgen's recommendation of discontinuation, the subject's decision to discontinue for any reason, or until an administrative decision is made to close the study).**

Subject disposition, demographics and baseline characteristics will be summarized.

Summary statistics for continuous variables will include the number of subjects, mean, median, standard deviation or standard error, minimum, and maximum. For categorical variables, the frequency and percentage will be given.

Subjects will be summarized according to whether subject rolled over from a parent study and their treatment allocation from a parent study when applicable.

For efficacy analyses, the baseline value is defined as:

- Subjects that participated in a qualifying parent study (including 20110233) and with baseline data from the parent study: the baseline is defined as the baseline of the qualifying parent study
- Subjects not enrolling from a parent study or without baseline data from the parent study: the baseline is defined as the baseline in this study

For non-efficacy analyses, baseline values for all subjects are defined as this study baseline values.

The percent change and absolute change from baseline in laboratory based exploratory endpoints at each scheduled visit will be summarized. Summaries of vital signs, ECGs, and anti-AMG 145 antibodies will be also provided.

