10.4.2.3 Exploratory Safety Analyses

Safety Laboratory Parameters

Laboratory parameters will be summarized using descriptive statistics at each measurement time point. Laboratory shift tables for certain analytes will be provided using the CTCAE v.4 toxicity criteria. The results will be based on the maximum (ie, worst) shift from baseline (starting of the exposure of AMG 145) to the end of study.

Vital Signs

Vital signs will be summarized using descriptive statistics at each measurement time point.

Electrocardiogram

RR, PR, QRS, QT, and QTc intervals will be summarized at each measurement time point. Frequency tables for maximal QTc and maximal change in QTc at post-dose period using the categories suggested in the ICH E14 guidelines will be provided by treatment group.

PK Parameters

Summary statistics of PK concentration and PCSK9 will be provided.

Anti-AMG 145 Antibodies

The incidence and percentages of subjects who develop anti-AMG 145 antibodies (binding and neutralizing) at any time will be tabulated.

Concomitant Medications

Concomitant medications of interest will be summarized.

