# 6.2 Demographics and Baseline Related Definitions

## Change (absolute change) from Baseline

The arithmetic difference between a post-baseline value and baseline for a given time point:

Change from baseline = post-baseline value – baseline value

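### SAP 6.1 gives rollover subjects the parent-study baseline without the protocol's efficacy limit or fallback, so their safety change tables would include parent-period change that SAP Section 11 does not declare

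*SAP*

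**What the plan says.** **SAP.** Section 6.1 (Baseline) sets one rule for rollovers: "For parent study rollover subjects, baseline is defined as the baseline of the parent study". The only exemption by parameter is: "For hemoglobin A1c, baseline is defined as the study 20110271 baseline for all subjects, as hemoglobin A1c was not collected in study 20110233". Section 6.2 defines change as "The arithmetic difference between a post-baseline value and baseline for a given time point", so every change table inherits the 6.1 rule. Sections 10.7.1 to 10.7.3 plan changes and shifts for laboratory values, changes for vital signs, and QTc change categories at 30 and 60 ms. None of them names its own baseline. Section 11 lists one departure from the protocol, on tabulating treatment-related adverse events.

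**Protocol.** Section 10.4.1 places the parent baseline under efficacy analyses, for subjects who have parent baseline data. For subjects with no parent study, or "without baseline data from the parent study: the baseline is defined as the baseline in this study". It then adds: "For non-efficacy analyses, baseline values for all subjects are defined as this study baseline values". The synopsis agrees: "For non-efficacy analyses, baseline values for all subjects are defined as the baseline values obtained in this study, 20110271". Section 10.4.2.3 describes the laboratory shift tables as the worst "shift from baseline (starting of the exposure of AMG 145) to the end of study", and also plans "Frequency tables for maximal QTc and maximal change in QTc at post-dose period".

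**The concern.** The two documents give different reference values for the same safety tables. Under the protocol, a rollover's safety change runs from entry into 20110271. Under SAP 6.1 it runs from the start of an earlier study, so it mixes change in this study with change in the parent study.

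This matters most for rollovers who were on placebo in the parent study. SAP 10.1 shows that such subjects were expected, because the interim analysis grouped 20110233 rollovers by AMG 145 or placebo. Assuming they received no AMG 145 elsewhere in the parent study, their parent-period change arose before any exposure, yet it would be tabulated as on-study safety change. The study has no control group against which that would show.

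The missing fallback is a second gap. SAP 9.3.1 imputes nothing, so a rollover without a parent value would drop out of change summaries that the protocol would complete from this study's baseline.

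**Working it through.** The plan gives no figure on this point. Its only design figures are confidence intervals for adverse event incidence, which do not depend on baseline. The check is a comparison of text, an identity, and a scale calculation on assumed inputs.

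**1. Same protocol version.** SAP Section 1 says that it implements Amendment 6 of 02 December 2015, which is the protocol supplied. An outdated protocol does not explain the difference.

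**2. Rules side by side, for a rollover subject.**

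| Output | Protocol baseline | SAP 6.1 baseline |
|---|---|---|
| Efficacy lipids, parent value exists | Parent | Parent |
| Efficacy lipids, no parent value | 20110271 | None defined |
| Change in safety labs, vital signs, QTc | 20110271 | Parent |
| HbA1c | 20110271 | 20110271 |
| Laboratory shift tables | Start of AMG 145 exposure, study not named | Parent |

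Shift tables and QTc change are named in protocol 10.4.2.3. The tables of change in safety labs and vital signs are SAP additions, to which the protocol's general non-efficacy rule applies.

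**3. What the HbA1c exemption implies.** SAP 4.3 lists HbA1c among the safety laboratory values. It is exempted because 20110233 did not collect it. Had 6.1 followed the protocol, all safety values would already use the 20110271 baseline and no exemption would be needed.

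**4. Effect on one subject.** Let B0 be the parent baseline, B1 the 20110271 baseline and V a later value.
- SAP change = V − B0
- Protocol change = V − B1
- Difference = B1 − B0 = d, the same at every visit for that subject

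In a mean at a given visit, the offset is f × (mean d among the rollovers contributing), where f is their share of the subjects in that column. Shift grades and QTc categories are assigned per subject, so the full d applies there. A QTc category changes whenever V − B1 and V − B1 + d fall on opposite sides of 30 or 60 ms. Protocol Appendix A schedules only one ECG after Day 1, at end of study or early termination, and SAP Table A.3 agrees. With no unscheduled tracing, the maximum change is therefore one value minus the baseline.

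**5. Shift tables.** Protocol 10.4.2.3 does not say in which study AMG 145 exposure starts.

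| Reading of exposure | Parent placebo | Parent AMG 145 |
|---|---|---|
| In this study | 20110271 baseline | 20110271 baseline |
| In the parent study | 20110271 baseline | Parent baseline |

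SAP 6.1 uses the parent baseline in all four cells. It agrees with 10.4.2.3 in one (parent AMG 145, parent-study reading) and differs in three: both placebo cells, and parent AMG 145 under the in-study reading.

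**6. Scale, on assumed inputs only.** Protocol 2.2.4 plans 59 subjects for 20110233, and protocol 3.3 plans 310 here. Counting 20110233 alone:
- 50% enter: 0.50 × 59/310 = 0.095
- 75% enter: 0.75 × 59/310 = 0.143
- 100% enter: 59/310 = 0.190

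Other parent studies would add to f. SAP 6.3 splits all tables by apheresis cohort, so f in each column will differ from these values, and it will also vary by visit as subjects leave. No value of d can be taken from the documents.

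**The case against.** **SAP 6.1 may have been written with efficacy in mind.** HbA1c is listed as a safety value in 4.3 but analysed in 10.6.2, next to lipids, PCSK9 and hsCRP. An author thinking only of the 10.6 endpoints would still have needed the exemption. This stands in part. A reader might infer that the exemption proves a parent baseline for all safety values. It is strong evidence, not proof. The wording of 6.1 remains unlimited all the same, and a programmer following it would use the parent value.

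**SAP 10.1 says that final analyses use data collected in this study.** That sits badly with a parent baseline and may point to loose drafting rather than a deliberate switch. It does not redefine baseline, though, and read strictly it would also bar the parent baseline for efficacy. It cannot serve as a limit for safety alone.

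**Protocol 10.4.2.3 may itself support the parent baseline.** For shift tables in parent-AMG 145 rollovers, it may. A reader might infer that SAP 6.1 contradicts the protocol for every rollover in those tables; the documents do not support that, because the specific clause is ambiguous and may override the general rule. It gives no support for parent-placebo rollovers and does not cover the other change tables.

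**The study is descriptive.** This is true, and it limits the weight. No test or decision depends on these tables. Nor do the documents identify any rollover or analyte, apart from the HbA1c already handled, that lacks a parent baseline.

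**Conclusion.** The point holds as a contradiction between the documents. SAP 6.1 omits the protocol's efficacy limit and its fallback, nothing later in the SAP restores them, and Section 11 is silent. As written, safety laboratory, vital-sign and QTc changes in rollovers carry an offset d that the protocol's rule excludes.

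For parent-AMG 145 rollovers, either reference is defensible: change since entry to this study, or change since parent baseline. The protocol chose the first for non-efficacy analyses, and the SAP moves to the second without saying so. For parent-placebo rollovers, neither document gives a reason for the parent baseline in safety tables.

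The size is unknown. The shares of 0.095 to 0.190 rest on assumed rollover fractions and show scale only. A reader might infer that the safety results as a whole, or the primary endpoint, are biased. The documents do not support that: SAP 6.3 defines treatment emergence from first dose in this study, so adverse event incidence does not use this baseline, and subjects from no parent study are unaffected. The correction should be made, but the primary analysis does not depend on it.

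**What to change.** - **SAP 6.1, efficacy.** Limit the parent baseline to the endpoints in 4.2 and the efficacy laboratory list in 4.3. Where a rollover has no parent value, use the 20110271 baseline.
- **SAP 6.1, safety.** For safety laboratory values (HbA1c included), vital signs and ECG, use the 20110271 baseline for all subjects, taken before first dose in this study. Values from the combined parent end-of-study/Day 1 visit qualify, as does the screening ECG for subjects who were screened.
- **Apheresis.** Keep the rule that the pre-apheresis value is used when both exist. A bare last-value-before-dose rule would not do: protocol Section 7 has blood drawn before and after apheresis, and Appendix A has AMG 145 given afterwards on the same day, so that rule could select a post-apheresis value.
- **hsCRP.** State which baseline it uses. SAP 10.6.2 plans change summaries and a shift table for it, but neither 4.2 nor the efficacy list in 4.3 names it.
- **SAP 10.7.1.** State one shift-table baseline, and say whether AMG 145 exposure starts in this study or in the parent study.
- **SAP Section 11.** If the parent baseline is kept for any safety summary, declare and justify it there.

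The cost is a few sentences of SAP text, re-derivation of the safety baseline for rollovers, and a rerun of the affected change, shift and QTc tables. No new data are needed, because protocol 7.1.1, 7.1.2 and Appendix A already schedule these assessments at screening or Day 1.

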#### First Dose Date of Investigational Product

For each subject, the First Dose Date of Investigational Product is defined as the first administration date of the IP in the extension study as recorded on the IP administration electronic Case Report Form (eCRF).

#### **Study Day 1 and Date**

For each subject, Study Day 1 is defined as the first day that protocol-specified investigational product is administered to the subject in the extension study. The date associated with Study Day 1 is the Study Day 1 Date.

#### Study Day

For each subject, and for a given study visit date, Study Day is defined as the number of days since Study Day 1:

Study Day = (study visit date - Study Day 1 date) + 1

If the date of interest is prior to the Study Day 1:

Study Day = study visit date – Study Day 1 date, so that the day prior to Study Day 1 is Study Day -1.

#### End of Investigational Product (EOIP) Date

For each subject, the end of AMG 145 is defined as the date of the last administration of investigational product. This date is recorded on the IP administration eCRF if the final dose was taken in-clinic, or on the non-clinic final IP dose date eCRF if non-clinic.

#### Parent End of Study Date

For each subject rolled over from a parent study, the Parent End of Study Date is the EOS date recorded on the parent End of Study eCRF.

#### End of Study (EOS) Date

For each subject, the end of study date is the date recorded on the End of Study eCRF of study 20110271.

#### Study End Date

The study end date is the last EOS date of all enrolled subjects.

Statistical Analysis Plan: 20110271

Dated: 26 May 2018 Page 11 of 27

# 6.2 Demographics and Baseline Related Definitions

## Change (absolute change) from Baseline

The arithmetic difference between a post-baseline value and baseline for a given time point:

Change from baseline = post-baseline value – baseline value

#### Percent Change from Baseline

The percent change from baseline for a given variable at a given time point is defined as:

100 x [(value at given time point – baseline value) / baseline value]

#### Baseline Metabolic Syndrome

For each subject without type 2 diabetes mellitus, metabolic syndrome is identified by the presence of 3 or more of the components listed below (modified AHA/NHLBI criteria). Subjects with type 2 diabetes cannot be categorized as having metabolic syndrome.

Risk Factor	Defining Level
Elevated waist circumference:	
Non-Asian:	
Men	≥ 102 cm
Women	≥ 88 cm
Asian:	
Men	≥ 90 cm
Women	≥ 80 cm
Triglycerides	≥ 150 mg/dL
HDL cholesterol	
Men	< 40 mg/dL
Women	< 50 mg/dL
Blood pressure	SBP ≥ 130 mmHg or DBP ≥ 85 mmHg
	OR Hypertension checked 'yes' on CV Medical History eCRF
Fasting glucose	≥ 100 mg/dL

# Baseline CHD Risk Factors 2 or more (yes/no)

A subject will be categorized as having 2 or more CHD Risk Factors (Y/N) from the list of the modified NCEP ATP III risk factors:

- current cigarette smoking
- hypertension
- type II diabetes mellitus

Statistical Analysis Plan: 20110271

Dated: 26 May 2018 Page 12 of 27

family history of premature CHD as recoded on the eCRF form

 low HDL-C defined as baseline HDL-C < 40 mg/dL in men and < 50 mg/dL in women.

## 6.3 Other Study Related Definitions

#### Analytical Study Week Assignments

Analytical windows will be used to assign parameters to study weeks. The algorithm is provided in Appendix A.

